## **3 STATISTICAL ANALYSES**

#### 3.1 GENERAL CONSIDERATIONS

The baseline values of efficacy parameters are generally defined as the last available value prior to the first dose of study medication unless otherwise specified. In most cases the assessment should be prior to the randomization call, but it is possible that some assessments are performed between the actual randomization call and the first intake of investigational medicinal product (IMP). For the Expanded Disability Status Scale (EDSS) score, the baseline value will be taken as the average of the screening and randomization visit values. If one of the values is missing, the non-missing value will be used as baseline. The baseline value of safety parameters is defined as the last available value prior to the first dose of IMP. For the C-SSRS, the baseline value will be the worst assessment between the past 6 months evaluation at screening and the C-SSRS since last visit evaluation on Day 1. For participants randomized but not treated, the baseline value is defined as the last available value before randomization. Unless otherwise indicated, 2-sided p-values and 95% confidence intervals (CIs) will be provided for treatment comparisons.

To include all participants in analyses where baseline Gd-enhancing T1-hyperintense lesion presence or absence is used as a covariate, baseline status (present or absent) will be imputed for participants with a missing baseline count: if subsequent post-baseline counts for a participant are all 0, then impute baseline status as absent, otherwise, impute baseline status randomly with seed = 16645 based on the proportion of presence/absence at baseline in the overall population. Of note, the number of participants affected is minimal with no impact on results.

In general, continuous data will be summarized using the number of observations available, mean, standard deviation (SD), median, interquartile range (Q1, Q3), minimum, and maximum. Categorical and ordinal data will be summarized using the count and percentage of participants. Efficacy data will be analyzed in the ITT population, and safety data will be analyzed in the safety population, unless specified otherwise.

Unless otherwise specified, analyses will be performed by treatment group and overall for baseline and demographics characteristics.

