- Dose regimen: 60 mg once daily

Investigational medicinal product(s)

• Formulation: placebo to match SAR442168 film coated tablet

VV-CLIN-0579238 21.0

- Route(s) of administration: oral
- Dose regimen: once daily

Noninvestigational medicinal product(s)

- Formulation: MRI contrast-enhancing preparations
- Route(s) of administration: intravenous (IV)
- Dose regimen: per respective label

Property of the Sanofi Group - strictly confidential

Temporary investigational medicinal product (IMP) interruption due to surgery

If surgery is needed during the study, consider the benefit-risk of withholding the IMP for at least 3 to 7 days pre- and post-surgery and the risk of bleeding.

Devices

Not applicable.

Long-term safety study

After the end of this study, participants who complete the trial and are taking the IMP treatment until the end of the trial (double-blind or open-label SAR442168 if meeting 6-month CDP) may be offered the option to participate in a long-term safety (LTS) study for an additional 2 years, or until SAR442168 is approved in their respective country, whichever comes first. Details of the LTS study will be described in a separate protocol.

Duration of study (per participant)

The duration of treatment will vary for individual participants, depending on the time of recruitment. Considering the recruitment period of approximately 24 months and an assumed event rate (discussed below), the duration of the study should be approximately 48 months. All recruited participants will be followed in the study until the common study end, which will be estimated and announced by the Sponsor to ensure that approximately 288 events of 6-month CDP have been observed before the study end.

Statistical considerations:

• Primary endpoint:

The primary estimand will be the treatment difference between SAR442168 and placebo in time to onset of 6 month-CDP regardless of completion of the treatment period. This estimand corresponds to a "treatment policy strategy". This estimand will be considered primary for supporting regulatory decision making.

The time to onset of 6-month CDP will be analyzed by a Cox proportional hazards model with terms for treatment, age at screening (>40, \leq 40 years), geographic region (US, non-US), baseline EDSS score, and baseline Gd-enhancing T1 lesions (0, \geq 1). A log-rank test stratified by age at screening (>40, \leq 40 years) and geographic region (US, non-US) to compare SAR442168 to placebo will also be examined.

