#### **Quantitative analyses**

For all laboratory variables, vital signs, and ECG variables above, descriptive statistics for results and changes from baseline will be provided for each analysis visit window during the DB treatment period and OL period respectively. These analyses will be performed using central measurements only for laboratory variables.

For each laboratory parameter, vital signs parameter and ECG parameter, mean changes from baseline with the corresponding SE will be plotted over time.

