#### Analyses according to PCSA

Potentially clinically significant abnormality (PCSA) analyses will be performed based on the PCSA list currently in effect at Sanofi at the time of the database lock. For parameters for which no PCSA criteria are defined, similar analyses will be done using the normal range.

Analyses according to PCSA (normal range) will be performed based on the worst value during the DB treatment-emergent period and OL period, using all measurements (either local or central, either scheduled, nonscheduled or repeated).

For laboratory variables, vital signs, and ECG variables above, the incidence of participants with at least one PCSA during the DB treatment-emergent period and OL period will be summarized respectively regardless of the baseline level and according to the following baseline status categories:

- Normal/missing
- Abnormal according to PCSA (normal range) criterion or criteria

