#### 3.6.3.2 Analysis of suicidality assessment

The number (%) of participants with suicidal ideation, suicidal behavior, and self-injurious behavior without suicidal intent based on the Columbia Suicide Severity Rating Scale (C-SSRS) during DB treatment period and OL period will be summarized respectively. A shift table for baseline versus during treatment and OL responses will be provided respectively according to the categories of no suicidal ideation or behavior, suicidal ideation, and suicidal behavior.

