#### Table 8 - Analysis window definition of safety variables

Note: Analysis windows in open-label period can follow the same rule except that the first open-label dose date is Day 1 in that period

	Taurat	Plasm samp (NfL), serum	na les n	0		Lymphoc	yte	Diacede		
AVISIT	Target Day	samp (Chi3l	les L1)	(lq levels)	mpies	flow cyto	flow cvtometrv		archiving	
		Start Day	Énd Day	Start Day	End Day	Start Day	End Day	Start Day	End Day	
Screening	-1							-40	-1	
Day 1	1	1	1	1	1	1	1			
Month 1	28									
Month 2	56									
Month 3	84	2	126							
Month 4	112									
Month 5	140									
Month 6	168	127	252	2	252					
Month 9	252									
Month 12	336	253	504	253	504					
Month 15	420									
Month 18	504									
Month 21	588									
Month 24	672	505	840	505	840					
Month 27	756									
Month 30	840									
Month 33	924									
Month 36	1008	841	1176	841	1176					
Month 39	1092									
Month 42	1176									
Month 45	1260									
Month 48	1344	1177	1386	1177	1386					
		Start Day: last visit window upper limit + 1; End Day: EOS visit date								
EOS		Nomina	ıl visit (9	000)						
		Start Da	ay: date	of discontinuat	ion + 1;					
		End Day: start of the next scheduled visit window								
pEOT		Map to the closest scheduled visit								

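### The SAP defines no open-label safety baseline, so three open-label displays compare placebo switchers with a value taken before randomized treatment, not before their first tolebrutinib dose

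*SAP*

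**What the plan says.** SAP 3.1 sets a single safety baseline: "The baseline value of safety parameters is defined as the last available value prior to the first dose of IMP". Protocol 9.4.1 has the same rule. The Protocol synopsis lists placebo among the investigational products ("Formulation: placebo to match SAR442168 film coated tablet"), and Protocol Table 2 classes it as IMP. The C-SSRS has its own rule in SAP 3.1: "the baseline value will be the worst assessment between the past 6 months evaluation at screening" and the Day 1 evaluation. Neither document gives an open-label baseline.

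Three planned open-label displays need a baseline:

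- **Laboratory, vital signs, ECG** (SAP 3.6.3.1, quantitative analyses): "descriptive statistics for results and changes from baseline will be provided for each analysis visit window during the DB treatment period and OL period respectively".
- **PCSA** (SAP 3.6.3.1): incidence in the double-blind and open-label periods, "summarized respectively regardless of the baseline level and according to the following baseline status categories".
- **C-SSRS** (SAP 3.6.3.2): "A shift table for baseline versus during treatment and OL responses will be provided respectively".

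Other parts of the plan treat the switch as a new start. SAP 3.1 makes the open-label phase a separate treatment-emergent period and shows its data by original arm as well as overall. The note under SAP Table 8 reads: "Analysis windows in open-label period can follow the same rule except that the first open-label dose date is Day 1 in that period". It resets the visit windows and does not mention baseline.

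**The concern.** Placebo switchers are the trial's second group of first-time tolebrutinib exposures, and they have their own column in the open-label tables. In that column the clock restarts at the first open-label dose but the reference value does not. A Month 3 change would be labelled as three months after first tolebrutinib, yet it would also contain whatever happened on placebo.

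The PCSA and C-SSRS displays have the same problem. An abnormality that began on placebo and persisted would count as an open-label PCSA in a participant with normal baseline. Suicidal ideation that first appeared on placebo, if still reported, would appear as a shift during open-label treatment. Such carry-over can overstate new abnormalities. Drift on placebo in the opposite direction can hide a change after the switch.

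This matters because Protocol 2.3 reports liver injury cases in Months 1 to 3 of treatment, so laboratory data soon after a first exposure will be read closely. The Kaplan-Meier liver analyses in SAP 3.6.3.1 are specified for the treatment-emergent period. For switchers, SAP 3.1 ends that period at the first open-label dose, so the open-label laboratory reading rests largely on the change and PCSA tables.

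**Working it through.** **1. The plan's own figure.** SAP 3.2.1 requires at least 154 days from onset to 6-month confirmation: 24 × 7 − 2 × 7 = 168 − 14 = 154. This reproduces exactly.

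**2. Shortest gap between baseline and first tolebrutinib dose in a placebo participant.** A switch requires 6-month CDP (Protocol 6.6.1 and 7.1.1). Onset may be seen at a quarterly or an unscheduled visit, but confirmation must be at a quarterly visit (Protocol 8.1.1.1, SAP 3.2.1). Visits fall at 84k ± 7 days, and a month is 28 days.

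| Onset | Rule | Earliest confirmation | Protocol months |
|---|---|---|---|
| Scheduled, Month 3 (day 84) | nominal | 84 + 168 = day 252 | 252/28 = 9.0 |
| Scheduled, early window edge (day 77) | 77 + 168 | day 245 | 245/28 = 8.75 |
| Unscheduled, day 2 | at least 154 days (2 + 154 = 156; the Month 6 window opens at 168 − 7) | day 161 | 161/28 = 5.75 |
| Unscheduled, day 2 | at least 168 days (2 + 168) | day 170 | 170/28 = 6.07 |

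The minimum is therefore about 6 protocol months. The early route is narrow. Under the 154-day rule, onset must be by day 14 for a Month 6 visit on day 168 (168 − 154), or by day 21 for a visit on day 175 (175 − 154). EDSS scores within 90 days of an adjudicated relapse cannot count as onset, which makes it narrower still. Nine months or more is the usual case. The first open-label dose follows confirmation, so these are lower bounds.

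**3. Typical gap and number of participants.** Inputs from Protocol 9.2 and SAP 4: 1290 randomized 2:1, so 1290/3 = 430 on placebo; 2-year placebo event rate 23.6%; 10% annual discontinuation; 24 months of enrollment and at least 24 months of follow-up.

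- Placebo hazard = −ln(1 − 0.236)/2 = 0.1346 per year.
- Assumptions: exponential onset moved up to the next 12-week visit; confirmation 168 days later; exponential dropout; follow-up uniform on 24 to 48 months. A participant counts if confirmation precedes both dropout and study end.

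| Follow-up months counted as | Placebo participants confirmed in time | Median | Quartiles | Mean |
|---|---|---|---|---|
| Calendar months | 99 to 100 of 430 | Month 21 | 15, 30 | 22.3 |
| 28-day months | 92 of 430 | Month 21 | 12, 27 | 21.0 |

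The 99 to 100 range comes from reading 10% discontinuation as a yearly probability or as a hazard. Month 21 is 21 × 28 = 588 days, and 588/365.25 = 1.6 years.

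**4. Age of the reference under an open-label baseline.** From the Protocol 1.3 schedule, most laboratory tests, vital signs and C-SSRS are quarterly, so the reference would normally be no more than about 84 days old. Liver tests are required before open-label start (Protocol 6.6.1). ECG is at Months 3, 6, 9, 12 and 24, then yearly. Weight and urinalysis are half-yearly from Month 12. For a switch at Month 21 the last scheduled ECG is Month 12 (21 − 12 = 9 protocol months earlier), and the last scheduled weight and urinalysis are Month 18 (3 protocol months earlier).

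**The case against.** **Much of the open-label safety reporting needs no baseline.** A reader might infer that all open-label safety results are measured from the wrong point. The documents do not support that. Raw values by window, PCSA incidence regardless of baseline and C-SSRS counts by period use no baseline value. Open-label adverse events are defined by what developed, worsened or became serious in the open-label period itself (SAP 3.6.2). Only the three displays are affected.

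**The liver is partly protected.** Protocol 6.6.1 requires liver tests before the switch and sets liver criteria that bar it, with some exceptions. A liver abnormality that began on placebo and persisted is largely screened out, so liver PCSA misclassification is limited. This does not cover hematology, creatinine, ECG, vital signs or C-SSRS, and it does not alter the change-from-baseline problem.

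**A common pre-treatment baseline is defensible.** It is free of study drug and the same for both arms. That is a good reason to keep it for participants randomized to tolebrutinib. It does not help placebo switchers, whose drug-free period runs up to the first open-label dose.

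**The intended rule may be different.** The Table 8 note lets open-label windows follow the same rule with the first open-label dose as Day 1, and Table 8 has Screening and Day 1 rows. A programmer could derive an open-label pre-dose value from that. The note concerns windows only, however, and SAP 3.1 followed literally gives different tables. The ambiguity itself has to be resolved.

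**The analysis is descriptive.** SAP 3.6 plans no safety testing. This stands: no estimate, alpha or power figure for efficacy is touched.

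**Conclusion.** The point holds for three displays. As the SAP is written, open-label change from baseline, PCSA by baseline status and the C-SSRS shift table use a reference from before randomized treatment. In placebo switchers that mixes change on placebo with change after first tolebrutinib exposure. The gap is at least about 6 protocol months, usually 9 or more, with a median near Month 21 (about 1.6 years).

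Two stronger readings should be resisted. Nine months is not a firm minimum, because onset may be recorded at an unscheduled visit. Month 21 or 22 is not almost two years, because a protocol month is 28 days.

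The 92 to 100 of 430 is an upper bound. It assumes constant hazards and the planned rates, and that every confirmed participant switches. Protocol 6.6.1 lets participants stay on blinded treatment or move to another approved therapy, applies liver and alcohol criteria, and leaves open-label supply to be set by country. It also assumes 1290 randomized. The plan allows about 1100, or roughly 367 on placebo.

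The change should be made, since it affects how first-exposure safety data are read. It does not bear on the primary conclusion.

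**What to change.** - **Baseline.** In SAP 3.1, define an open-label baseline as the last available value before the first open-label dose.
- **Use.** Apply it to the three displays for participants randomized to placebo. Keep the original baseline for those randomized to tolebrutinib.
- **Overall column.** State which baseline it uses; showing the original baseline there is one option.
- **C-SSRS.** Define its open-label reference separately, for example as the last since-last-visit assessment before the first open-label dose. The present C-SSRS baseline includes a 6-month look-back, so the two shift tables will not be like for like, and a footnote should say so.
- **Table 8.** Align the note with the new definition, so that Day 1 and baseline have the same anchor in the open-label period.

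The cost is a few lines of SAP text and one derived flag, with no new data collection. The drawback is that the open-label reference for ECG, weight and urinalysis may be several months old, and up to a year for ECG. It would still be closer to the first tolebrutinib dose than the value from before randomization.

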#### **Observation** period

The observation periods for safety will be divided into 4 epochs:

- The screening (pre-treatment) period is defined as the period from the signed informed consent date up to first administration of the study intervention.
- The **treatment period** (ie, treatment-emergent (TE) period) is defined as the period from the first administration of study intervention to
  - The earlier of last administration of the study intervention + 10 days or first IMP in the LTS study for participants not receiving tolebrutinib OL treatment,
  - The first administration of tolebrutinib OL treatment for participants switching to OL therapy

- The **OL period** (ie, OL TE period), applicable only for participants switching to tolebrutinib OL treatment, is defined as the time from first administration of tolebrutinib OL treatment to the earlier of last administration of OL treatment + 10 days or first IMP in the LTS study
- The **post-treatment period**, if applicable, is defined as the period from the end of treatment period (or end of OL period, if applicable) to the participant's final post-treatment study contact date.

Summaries of OL period data will be presented by original randomized treatment group and overall.

The on-study period is defined as the time from randomization until the end of the study defined as the last scheduled visit for those who completed the study and the end-of-study date collected on electronic case report form (e-CRF) page "Completion of End of Study" for those who did not complete the study. If death is the end-of-study reason, date of death will be used.

## *Contingency measures for a regional or national emergency that is declared by a governmental agency*

Participants in Ukraine, Russia and Belarus who are lost to follow-up due to national emergency will be considered as prematurely discontinuing the study at the date of last contact (or start of war). For the primary endpoint of time to onset of 6M-CDP, unless already having a confirmed event at the time of last follow-up, participants will be censored at the date of the last EDSS assessment for the primary analysis. Other time-to-event endpoints will be handled similarly. For continuous endpoints as well as safety data, all observed data up to the last contact date will be included for assessment. For count data, all observed data up to the last contact date will be included in the analysis. No imputation will be performed for unobserved data/events that may happen after being lost to follow-up.

#### 3.2 PRIMARY ENDPOINT(S) ANALYSIS

#### 3.2.1 Definition of endpoint(s)

Time to onset of 6-month CDP is defined as the time from randomization to the onset of a sustained increase from baseline in EDSS score (of  $\geq 1.0$  point from the baseline EDSS score when the baseline score is  $\leq 5.0$ , of  $\geq 0.5$  points when the baseline EDSS score is  $\geq 5.0$ ) confirmed after a minimum 6-month interval.

EDSS scores used for potential onset of disability progression may be observed by the Examining Investigator during routine quarterly visits or unscheduled visits. However, confirmation of CDP (after at least 6 months) must be at a routine quarterly visit (with the potential exception in case of contingency measures for a regional or national emergency). Results of all EDSS assessments obtained during routine or unscheduled visits throughout the minimum 6-month period (for the primary endpoint) will serve as the basis for conclusion. Once confirmation is achieved, the potential onset becomes the actual onset for time to onset of CDP.

In case of occurrence of adjudicated relapse, only EDSS assessments measured more than 90 days after relapse onset will be used to determine onset of disability progression. In addition, for the purpose of confirmation, only EDSS scores measured more than 90 days after the onset of an adjudicated relapse will be used. In case of such multiple sclerosis (MS) relapse, the next quarterly EDSS assessment >90 days after relapse onset will be used for CDP confirmation. The minimum increase in score required for progression must also be maintained for any non-confirmatory (ie, intervening) EDSS assessment(s) between the initial (onset) and confirmation EDSS scores.

Note: 6-month confirmation must be  $\geq 154$  days after onset. Given that visits are scheduled every 12 weeks with a time window of  $\pm$  7 days for conducting EDSS assessment, the minimum per protocol allowed time between 2 EDSS assessments scheduled 24 weeks apart is 154 days (6 months = 24 weeks = 168 days minus a 7-day window for each of the 2 visits, ie, 168 - 14 = 154).

#### 3.2.2 Main analytical approach

The primary analysis of the primary endpoint, time to onset of 6-month CDP, will be performed on the ITT population. The null hypothesis is no treatment difference between tolebrutinib and placebo, and the alternative hypothesis is that there is a between-treatment difference. The study will be declared positive if the null hypothesis for the primary endpoint of 6-month CDP for tolebrutinib compared to placebo is rejected at the 2-sided 0.05 significance level.

#### In this primary ITT analysis:

- For participants who complete the study without an initial onset of disability progression, the participant will be censored at the date of last EDSS assessment.
- For participants who have an initial onset of disability progression but complete the study without 3-month confirmation, the participant will be censored at the date of last EDSS assessment.
- For participants who prematurely discontinue the study before 6-month confirmation of an onset of disability progression, regardless of having an initial onset, the participant will be censored at the date of last EDSS assessment.
- For participants who complete the study, meet 3-month CDP criteria, and continue to meet criteria for EDSS disability progression through the final study assessment, but do not reach 6-month confirmation, the 6-month CDP event status of the participant will be determined by an imputation approach. The details of this imputation approach are provided in Section 3.2.3.

